### 8.2 Randomisation, blinding and treatment allocation

No randomization will be applied. The Dutch, Slovenian and Greek patients will receive the MMC with PGx testing. The German patients will get access to the MMC, but will not receive any PGx testing. We will test the user experience.

#### 8.3 Study procedures

See also Section 3. Patients matching inclusion criteria as described in Section 3 will be invited to participate. If a patient agrees and provides IC, they are asked to complete a baseline questionnaire (table 1). All patients will be provided access to the MMC. In The Netherlands, Greece and Slovenia, 10 ml blood will be collected during a venipuncture or with saliva using saliva collection kits designed for DNA purification. The participants will then be genotyped for *CYP2C9, CYP2C19, CYP2D6,* and *SLCO1B1*. All participants will gain access to the MMC, where participants that are genotyped will receive the PGx results. Questionnaires collecting data on the patient experience, clinical monitoring, clinical outcome, and adverse events will be collected at 2 and 12 weeks through the eClinical Data Management Platform Castor, for which the patients receive an email. The questionnaire and genetic information will be used for the descriptive statistical analysis of the main study endpoints.

### 8.4 Withdrawal of individual subjects

Subjects can leave the study at any time for any reason if they wish to do so without any consequences. The investigator can decide to withdraw a subject from the study for urgent medical reasons.

### 8.4.1 Specific criteria for withdrawal (if applicable)

Not applicable, there are no specific criteria for withdrawal. The national principal investigator can decide to withdraw a subject from the study for urgent medical reasons.

The eCRF will have a specific page that enables the type of withdrawal to be classified precisely, and where possible the individual reason to be documented. Types of withdrawal from which can be selected:

- Complete withdrawal (none of the patient's data can be used, e.g., because the subject wants to fully withdrawal/wrong initial drug etc.)
- Withdrawal from remaining follow-up only (patient consents for the study to use their data which has already been collected, but they decline to continue to be followed-up OR patient did not use index drug for at least 7 consecutive days)
- Lost to follow-up (the subject does not specify that they decline further follow-up, they are unable to be contacted)
- Partial withdrawal (e.g., withdraw from ever using the patient-reported online monitoring system, but happy to be contacted by research team)
- Death

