# 3. STUDY DESIGN

## 3.1 Overall study design

This study is a multi-centre, open-label study to assess the impact of the developed MMC in combination with the developed risk score algorithms, patient-reported outcome tool, and model-based precision dosing tool on patient empowerment of polypharmacy patients, thereby improving drug safety. In the study, a total of 120 patients will be enrolled in The Netherlands, Greece, Slovenia, and Germany (30 patients per country). The study subjects will be followed for 12 weeks. At set time intervals (2 and 12 weeks) the subjects will be asked to complete a validated questionnaire through the eClinical Data Management Platform Castor (table 1), for which the patients receive an email and a reminder through the MMC. These questionnaires collect information on the experience with the MMC, clinical monitoring, clinical outcome, and adverse events.

Table 1. Overview of the questionnaires during the 12-week follow-up. The baseline questionnaire comprises of 97 questions, the 2-week questionnaire of 133 questions and the 12-week questionnaire of 206 questions. All questionnaires are adaptive.

	Baseline questionnaire	Adaptive questionnaire in the MMC at time point:	
		2 weeks	12 weeks
Experience			
Usability		Х	х
Health literacy	х		х
Clinical monitoring			
Comorbidities and allergies	х		
Concurrent medication and herbal	х	х	х
remedies (through patient diary)			
Clinical outcome			
Drug adherence	х	Х	х
Quality of Life	х		х
Adverse events			
Patient reported ADR		Х	х
Assessment of ADR severity		х	х
Pharmacogenomics			
DNA sample collection	Х		

The baseline questionnaire will additionally comprise questions covering in- and exclusion criteria, demographics, recruitment information, previous PGx test results, comorbidities and allergies, and the level of health literacy before use of the MMC. In total, the baseline questionnaire consists of 97 questions. The questionnaire offered two weeks after inclusion in the study consists of 133 questions. The last questionnaire, offered 12 weeks after inclusion in the study, consist of 206 questions. All questionnaires are adaptive meaning that the length and duration of the questionnaire depends on the answers of the participants.

[figure not shown]

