# 3.3 Data collection procedures

T=0 is defined as the day the patient initiates the index drug (table 3). During the 12-week follow-up period, the patients will receive surveys at baseline, 2 weeks and 12 weeks and a semi-structured close-out interview at week 12. Patients are requested to complete the surveys within a week. In case a patient discontinues the index drug within the 12-week follow-up period, the follow-up will continue as initially anticipated. The questionnaires will be provided to the patients through the medication management centre.

The data collected by the surveys is summarized in table 2. The MMC will collect: 1) Data entered by patients: demographic information, medical information, symptom diary, 2) Data created by the MMC and its tools: medication plan assessed with its safety risks (DDIs, DGIs, risk score, dosing information) and 3) statistical information collected by the system about the usage of the system by individual patients, sub-cohorts and the whole cohort.

All data will be entered into an electronic Case Report Form (eCRF), which guarantees consistency of data collection procedures. Data will be used exclusively in a pseudonymous fashion and data protection will be guaranteed according to international regulations. Local, independent internal monitors will guarantee data integrity and data homogeneity across all four implementation countries by risk-based monitoring of a random sample of the collected data. The research team will collect and store patient contact information (e-mail address, telephone number, name, and study-ID number) in a separate, local file (national subject identification code list).

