# 5.1.2 Questionnaires

The baseline questionnaire will comprise questions regarding demographics, in- and exclusion criteria, and comorbidities. Additionally, standardized questionnaires will be offered to the patients at 2 and 12 weeks after initiation of the index drug to obtain information about health behaviour, drug use, ADRs (PRO-CTCAE), quality of life (SF-36), MMC experience and health literacy (HLS-EU-Q47). The questionnaires are adaptive meaning that based on the provided answers only relevant follow-up questions will be asked to minimize the burden. Lastly, a semi-structured close-out interview will be held at week 12 to gather information on the experience with the MMC.

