#### 8. METHODS

### 8.1 Study parameters/endpoints

### 8.1.1 Main study parameter/endpoint

Proof of principle-study focused on assessing the impact of the developed MMC on patient empowerment in polypharmacy patients in order to improve drug safety. The primary endpoint is the sense of empowerment and health literacy for participants before and after use of the MMC. The endpoint consists of:

- Patient capacities, beliefs or resources including self-efficacy, sense of meaning and coherence about their condition, health literacy, perceived control and feeling respected by their healthcare providers.
- Activities or behaviours (things patient do) e.g., participate in shared decision-making by taking an active role and making informed decisions about their health and healthcare, self-manage and monitor their condition by choosing meaningful and realistic goals and taking steps to achieve those goals, participate in collective activities such as patient support or advocacy groups, and search for information about their health condition e.g., on the internet.

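### The eCRF withdrawal list lets a site end follow-up because the index drug was not used, while section 3.3 says follow-up continues after the drug is stopped

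*Protocol*

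**What the plan says.** Section 3.3 of the protocol sets the rule for patients who stop the index drug: "In case a patient discontinues the index drug within the 12-week follow-up period, the follow-up will continue as initially anticipated". It states no exception.

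Section 8.4.1 opens with "Not applicable, there are no specific criteria for withdrawal" and adds only that the national principal investigator may withdraw a subject for urgent medical reasons. It then says "The eCRF will have a specific page that enables the type of withdrawal to be classified precisely" and lists the types. The follow-up-only type covers a patient who allows use of data already collected but declines more follow-up. It also covers, joined by OR, the case where the "patient did not use index drug for at least 7 consecutive days".

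The affected outcome is defined in section 8.1.1: "The primary endpoint is the sense of empowerment and health literacy for participants before and after use of the MMC". Health literacy (HLS-EU-Q47) serves there as the proxy for empowerment. Table 1 in section 3.1 marks health literacy at baseline and 12 weeks only, patient-reported ADRs at 2 and 12 weeks, and adherence at all three times.

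**The concern.** A patient who starts the index drug, stops it, and is willing to go on answering questionnaires is kept in follow-up by section 3.3 and can be coded out of it under section 8.4.1. Nothing in the protocol says which text prevails, and four sites with different clinical settings may decide differently.

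The intervention is access to the MMC (section 5.1), not the index drug. A patient who has stopped the drug can still use the MMC and report health literacy, so ending data collection at that point discards an outcome that was obtainable. The loss would fall only on patients who stopped the drug, and some may have stopped because of an ADR. ADEs and drug cessation with its reason are both secondary outcomes (section 8.1.2). Section 8.5 does not replace these patients, because replacement is limited to loss to follow-up before the first questionnaire. Section 8.6 leaves missing data to the SAP, but no analysis can recover a questionnaire that was never sent.

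**Working it through.** **1. The texts applied to each kind of patient.** The 7-day phrase can mean (a) a gap of 7 or more days without the drug, or (b) never completing 7 consecutive days of use.

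| Patient, willing to continue | Section 3.3 | Section 8.4.1, reading (a) | Section 8.4.1, reading (b) |
|---|---|---|---|
| Starts, stops before 7 days of use, stays off 7 or more days | Continue | Can be coded out: conflict | Can be coded out: conflict |
| Starts, uses for 7 days or more, then stops for 7 or more days | Continue | Can be coded out: conflict | Not caught |
| Pauses 7 or more days and resumes | Not expressly covered | Can be coded out | Depends on use before the pause |
| Never takes the drug | Not covered (nothing was discontinued) | Can be coded out | Can be coded out |

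Both readings conflict with section 3.3 for some patients who started and stopped. Reading (a) reaches more of them. Patients who never took the drug are outside the conflict; section 4.2 requires that use has started.

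**2. Fit with the rest of the withdrawal text.** Section 8.4 gives two routes out: the subject's wish, or the investigator's decision for urgent medical reasons. Section 8.6 offers follow-up-only withdrawal as a choice for the participant. Seven-day non-use is neither.

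**3. What is lost if the code is applied.**
- On the Table 1 schedule: the week-12 health literacy score, which is the only post-baseline one, so the before/after comparison cannot be made for that patient.
- On section 5.1.2, "standardized questionnaires will be offered to the patients at 2 and 12 weeks after initiation of the index drug", with HLS-EU-Q47 among the instruments named: a patient coded out after week 2 might keep a week-2 score but would still lose week 12.
- The remaining ADR and adherence surveys: week 12, and also week 2 if follow-up ends before it.
- Data already collected, including diary reports, are kept.

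**4. Size.** The protocol states no discontinuation, dropout or power figure, so there is no figure of its own to reproduce. Inputs: N = 120, 30 per site (section 3.1).

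- Per patient: 1/120 = 0.83% of the cohort's week-12 scores; 1/30 = 3.33% of a site's.
- Illustration, with d an assumed share coded out: missing = d × N. The worst-case 95% half-width for the proportion classed as empowered is 1.96 × √(0.25/n), where n = N × (1 − d).

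| d (assumed) | Missing of 120 | Left | Half-width, cohort | Missing of 30 | Left | Half-width, site |
|---|---|---|---|---|---|---|
| 0 | 0 | 120 | 8.9 points | 0 | 30 | 17.9 points |
| 10% | 12 | 108 | 9.4 points | 3 | 27 | 18.9 points |
| 20% | 24 | 96 | 10.0 points | 6 | 24 | 20.0 points |
| 30% | 36 | 84 | 10.7 points | 9 | 21 | 21.4 points |

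Even at 30% the cohort half-width grows by only about 1.8 points (10.7 − 8.9). Precision is not the main issue; the selective nature of the loss is.

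**The case against.** The strongest reply is that section 8.4.1 gives no order to withdraw anyone. It disclaims specific criteria and then describes a page for classifying withdrawals. Who may end participation is set in section 8.4, and the only directive about stopping the drug is in section 3.3. On this view there is one clear rule and one badly worded menu option. This stands in part: the data loss depends on a site using the option. It does not remove the conflict, because the option's second ground is a fact about drug use and not a patient's decision. A site cannot select it for a willing patient and also comply with section 3.3.

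A second reply is that, on reading (b), the phrase is a minimum-exposure exception to section 3.3. That is possible, but section 3.3 states no exception, section 8.4.1 does not refer to it, and no purpose for such an exception is given. If an exposure condition is wanted, it can be met in the analysis without ending questionnaires.

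It is also fair that the 10% to 30% range has no basis in the protocol, that the analysis is descriptive (section 10) with no power claim (section 4.4), and that precision barely changes. All of this stands, and it is why the size is given per patient and the range only as illustration. Whether HLS-EU-Q47 is given at week 2 is a separate discrepancy and is not needed for the conclusion.

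**Conclusion.** The concern holds. Sections 8.4.1 and 3.3 contradict each other for patients who started and then stopped the index drug, on either reading of the 7-day phrase. That part is certain from the text.

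The consequence is conditional on a site applying the code. Each use costs one week-12 primary score (0.8% of the cohort, 3.3% of a site) from a patient who has not declined. How often this would happen cannot be derived from the protocol. No size or direction of bias is claimed for the primary outcome or for the ADE comparison with historical controls. It should be corrected, because the loss is avoidable, falls on a particular group of patients, could differ by site, and cannot be repaired afterwards.

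**What to change.** Reconcile sections 8.4.1 and 3.3 for questionnaire collection:

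- Remove non-use of the index drug as a ground for the follow-up-only withdrawal type.
- Record it as drug cessation with its reason, already a secondary outcome in section 8.1.2.
- Continue the planned questionnaires to week 12 unless the patient declines or another listed withdrawal type applies.
- If a 7-day exposure flag is wanted, define it (a 7-day gap, fewer than 7 days of use, or never started) and keep it as an analysis variable that does not end follow-up.
- While the text is open, state whether HLS-EU-Q47 is given at week 2, since Table 1 and section 5.1.2 differ.

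This concerns data collection only and does not touch treatment or the patient's right to leave. The cost is a short protocol amendment, notified to the METC if substantial (section 12.3), and a change to one eCRF option. For patients who stop the drug, the questionnaires are already planned under section 3.3.

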# 8.5 Replacement of individual subjects after withdrawal

Individual subjects will not be replaced after withdrawal, unless the participant is loss-to-followup before the first questionnaire.

# 8.6 Follow-up of subjects withdrawn from treatment

If a patient does not reply to attempts of contact, every effort will be made to contact the patient. If a patient wishes to withdraw, the reason for discontinuation will be noted, if the patient agrees. The date and reason (if disclosed) will be noted in the eCRF. How missing data is handled in the analyses will be described in the statistical analysis plan.

Participants will be given two options: 1) complete withdrawal, 2) withdrawal from follow-up only. Additionally, we can offer the patients the choice whether or not to report the PGx results back to them.

# 8.7 Premature termination of the study

The study will be terminated prematurely when the safety of participants cannot be guaranteed. No additional safety issues are expected in the study, and therefore no criteria have been Version number: 6, January 22nd, 2025 28 of 44 defined for premature termination of the study. When terminated prematurely the participants will be informed and the PGx results will be shared with the Dutch, Greek and Slovenian participants.

# 9. SAFETY REPORTING

# 9.1 Temporary halt for reasons of subject safety

In accordance with section 10, subsection 4 of the WMO, the sponsor will suspend the study if there is sufficient ground that continuation of the study will jeopardise subject health or safety. The sponsor will notify the accredited METC without undue delay of a temporary halt including the reason for such an action. The study will be suspended pending a further positive decision by the accredited METC. The investigator will take care that all subjects are kept informed.

# 9.2 AEs and SAEs

# 9.2.1 Adverse events (AEs)

AEs reported by the patient will be followed up until they have abated, or until a stable situation has been reached, as done within the realm of routine clinical care. AEs will be monitored via patient reporting through the medication management centre.

# 9.2.2 Serious adverse events (SAEs)

A serious adverse event is any untoward medical occurrence or effect that

- results in death;
- is life threatening (at the time of the event);
- requires hospitalization or prolongation of existing inpatients' hospitalization;
- results in persistent or significant disability or incapacity;
- is a congenital anomaly or birth defect; or
- any other important medical event that did not result in any of the outcomes listed above due to medical or surgical intervention but could have been based upon appropriate judgement by the investigator.

An elective hospital admission or prolongation of hospitalization will not be considered as a serious adverse event.

All national principal investigators have the responsibility for safety within their own country. The local investigators will report SAEs to the national principal investigators, who in turn will report it to their national spontaneous reporting system within 7 days of first knowledge SAEs that result in death or are life threatening followed by a period of maximum of 8 days to complete the initial preliminary report. All other SAEs will be reported within a period of maximum 15 days after the sponsor has first knowledge of the serious adverse events.

# 9.3 Follow-up of adverse events

All AEs will be followed until they have abated, or until a stable situation has been reached. Depending on the event, follow up may require additional tests or medical procedures as indicated, and/or referral to the general physician or a medical specialist. SAEs need to be reported till end of study, as defined in the protocol.

# 9.4 Data Safety Monitoring Board (DSMB) / Safety Committee

The MMC is not designed for the patients to adjust their treatment on their own. Rather, it is a collection of curated, publicly available information tailored to their personal polytherapy. Additionally, it is up to the healthcare providers to follow the DPWG guidelines and incorporate PGx testing results into their prescriptions. Therefore, no additional safety issues are expected.

### **10. STATISTICAL ANALYSIS**

# 10.1 Primary study parameter(s)

Descriptive statistics will be used to describe the primary outcome.

## **10.2 Secondary study parameter(s)**

Descriptive statistics will be used to describe the secondary outcomes.

### **11. ETHICAL CONSIDERATIONS**

#### **11.1 Regulation statement**

The EmPaSafe study will be conducted according to the study protocol, applicable regulatory requirements, the ethical principles of the Declaration of Helsinki (2013, see for the most recent version: www.wma.net) and in accordance with the Medical Research Involving Human Subjects Act (WMO), and in accordance with national law and legislation.

#### 11.2 Recruitment and consent

It is the responsibility of the national Principal Investigators to obtain ethical approval or favourable opinion in writing of the study protocol and protocol amendments, the patient information leaflet, and the informed consent form from the before enrolment of any subject into the study.

Recruitment will differ per site. In the Netherlands, recruitment will involve the LANA pharmacies as well as the outpatient pharmacy of the Leiden University Medical Center (LUMC). All participating pharmacies will receive information about the study during a site initiation visit. Pharmacies will identify eligible polypharmacy patients and pharmacies will identify eligible polypharmacy patients and verbally inform eligible patients about the EmPaSafe study. If patients are interested to participate, the pharmacy will provide the patient information leaflet. Within 2 work days, a researcher from the LUMC will call the patient to provide further information about the study and answer questions. Upon agreement by the patient, an ICF will be provided. The patient inclusion will be managed by the LUMC research team. The study team is also available for any questions both during recruitment and throughout the study.

#### 11.3 Benefits and risks assessment, group relatedness

Subjects undergo a small, extra burden. Firstly, 10 ml additional blood will be collected during a venipuncture. Secondly, subjects have to complete questionnaires at T=0, T=2 and T=12 (T in weeks). Lastly, the subjects will be contacted at T=12 for a close-out interview. No extra visits to the clinic are necessary.

Benefits to subjects in the study include having access to the medication management centre for the duration of the study. Additionally, Dutch, Greek and Slovenian participants will receive their PGx profile. This can be used to individualize drug treatment, based on the DPWG guide-lines.

Overall, minimal risks are expected for subjects as they will receive normal treatment.

# **11.4 Compensation for injury**

The investigator has a liability insurance which is in accordance with article 7 of the WMO. The sponsor (also) has an insurance which is in accordance with the legal requirements in the Netherlands (Article 7 WMO). This insurance provides cover for damage to research subjects through injury or death caused by the study. The insurance applies to the damage that becomes apparent during the study or within 4 years after the end of the study. The METC LDD did provide liberation of the subject insurance.

